8.4.1 Tumor Measurement

See 7.1.7 for details of tumor measurement and response assessment.

9.0 ADVERSE EVENTS

9.1 Definitions

9.1.1 Adverse Event (AE)

An adverse event (AE) is any untoward medical occurrence (e.g., an abnormal laboratory finding, symptom, or disease temporally associated with the use of a drug) in a subject or clinical investigation subject administered an investigational product and which does not necessarily have a causal relationship with this treatment. An AE can therefore be any unfavorable and unintended sign, including an abnormal laboratory finding, symptom, or disease temporally associated with the use of a medicinal product, whether or not related to the medicinal product.

Hospitalization for elective surgery or routine clinical procedures that are not the result of an AE (e.g., surgical insertion of a central line) need not be considered AEs and should not be recorded as such. Disease progression should not be recorded as an AE unless the investigator deems it attributable to the study therapy.

9.1.2 Suspected Adverse Reaction (SAR)

A suspected adverse reaction (SAR) is any AE for which there is a *reasonable possibility* that the investigational product is the cause. *Reasonable possibility* means that there is evidence to suggest a causal relationship between the drug and the AE. An SAR implies a lesser degree of certainty about causality than an adverse reaction, which means any AE caused by an investigational product.

Causality assessment to a study drug is a medical judgment made in consideration of the following factors: temporal relationship of the AE to study investigational product exposure, known mechanism of action or side effect profile of study treatment, other recent or concomitant drug exposures, normal clinical course of the disease under investigation,

and any other underlying or concurrent medical conditions. Other factors to consider in determining if a study drug caused the AE include:

- Single occurrence of an uncommon event known to be strongly associated with investigational product exposure (e.g., angioedema, hepatic injury, Stevens-Johnson Syndrome).
- One or more occurrences of an event not commonly associated with investigational product exposure, but otherwise uncommon in the population (e.g., tendon rupture). Often more than one occurrence from one or multiple studies would be needed before the sponsor could determine that there is *reasonable possibility* that the investigational product caused the event.
- An aggregate analysis of specific events observed in a clinical trial that indicates the events occur more frequently in the investigational product treatment group than in a concurrent or historical control group.

9.1.3 Unexpected AE or SAR

An AE or SAR is considered unexpected if the specificity or severity of it is not consistent with the applicable product information (e.g., Investigator's Brochure for an unapproved investigational product or package insert/summary of product characteristics for an approved product). Unexpected also refers to AEs or SARs that are mentioned in the Investigator's Brochure as occurring with a class of drugs/ investigational product or as anticipated from the pharmacological properties of the drug but are not specifically mentioned as occurring with the particular drug product under investigation.

9.1.4 Serious AE or SAR

An AE or SAR is considered serious if, in the view of either the investigator or sponsor, it results in any of the following outcomes:

- Death
- Is life-threatening (places the subject at immediate risk of death from the event as it occurred)
- Requires inpatient hospitalization (>24 hours) or prolongation of existing hospitalization (hospitalization for anticipated or protocol specified procedures such as administration of chemotherapy, central line insertion, metastasis interventional therapy, resection of primary tumor, or elective surgery, will not be considered a serious AE/SAR)
- Results in congenital anomaly/birth defect
- Results in a persistent or significant incapacity or substantial disruption of the ability to conduct normal life functions
- Important medical events that may not result in death, be life threatening, or require hospitalization may be considered a serious study treatment-related AE/SAR when, based upon appropriate medical judgment, they may jeopardize the subject or require medical or surgical intervention to prevent one of the outcomes listed in the definition (for reporting purposes, also consider the occurrences of pregnancy as an event which must be reported as an important medical event)

Pregnancy that occurs during the study must also be reported as a serious AE/SAR.

9.2 Documentation of non-serious AEs or SARs

For non-serious AEs or SARs, documentation must begin from day 1 of study treatment and continue through the 30-day follow-up period after treatment is discontinued.

Collected information should be recorded in the eCRF for that subject. Please include a description of the event, its severity or toxicity grade, onset and resolved dates (if applicable), and the relationship to the study drug. Documentation should occur at least monthly.

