3.0 STUDY ENDPOINTS

3.1 Primary Endpoint

Safety will be classified and graded by non-hematologic Grade ≥ 3 AEs (CTCAE v5.0) and treatment-related mortality through twelve weeks from the start of rituximab with or without etoposide therapy.

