3.2 Secondary Endpoints

3.2.1 At study entry, basic demographics and baseline laboratory values will be summarized using descriptive statistics (i.e., means, medians, and variability measures for continuous variable; rates and proportions for binary variables). Screening assessments to be completed within 21 days prior to study enrollment.

3.2.2 Overall survival will be assessed at 12 weeks, one year, and two years from the start of treatment.

3.2.3 Event-free survival will be defined as the rate of refractory disease, relapse (same definition of active disease as in the inclusion criteria in section 4.1), non-Hodgkin lymphoma development or death and will be assessed at 12 weeks, one year, and two years from the start of treatment.

3.2.4 Clinical response rate at end of treatment and 12 weeks from treatment initiation (clinical response defined as resolution of presenting signs/symptoms that defined

the Multicentric Castleman disease (MCD) attack) without relapse at 12 weeks. MCD attack/flare is defined in Section 4.1.1.

3.2.5 Radiologic response rate is the percentage of patients without relapse at end of treatment and 12 weeks from treatment initiation. Chest radiography and abdominal sonography will be used for staging. Per Revised response criteria for gross lymphadenopathy, response will be evaluated via complete survey of lymph nodes with measurements and physical assessment of other palpable masses with measurements.

Response criteria for lymph node response will be as follows: Complete response (CR)- disappearance of all evident disease; Partial response (PR)-at least 50% decrease in target lesions with no increase in non-target lesions, Stable disease (SD)- Neither sufficient shrinkage to qualify for PR nor sufficient increase to qualify for progressive disease (PD); PD- appearance of a new lesion or at least a 50% increase in lesion size.

3.2.6 Additional safety assessment will be graded by CTCAE v 5.0 through 12 weeks from the start of therapy.

3.2.7 Kaposi sarcoma exacerbation will be defined as new symptoms attributed to KS or clinically evident exacerbation of dermatologic or visceral disease. All disease flares will be biopsy confirmed whenever possible.

3.2.8 Quality of life will be assessed by the MCD symptom score, a patient-reported outcomes questionnaire, and PROMIS Global 10, at baseline (week 1), 15 days (week 3), end of treatment (week 5), 12 weeks, 6 months, and 24 months after treatment, and at the time of any relapse.

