8.0 EVALUATIONS AND ASSESSMENTS

8.1 Time and Events Table (Table 7)

Table 7: Time and Events Table.	Initial Visit or Relapse ¹	Treatment days 1, 8, 15, and 22 ²	End-of-treatment (Week 5)	Follow-up (12 weeks)	Long term follow up ⁴
Informed consent	Initial visit only				
History & physical exam ⁵	X	X	X	X	X
Concomitant medications ⁶	X	X	X		
ECOG performance status ⁷	X	X	X		
Toxicity evaluation ⁸	X	X	X	X	X ⁸
Tumor biopsy ⁹	X				
Survival ¹⁰		X	X	X	X
Treatments ¹¹		X			
Lymph node measurements	X	Day 15 only	X	X	X
MCD-SS and Quality of life assessment ¹²	X	Day 15 only	X	X	X ¹²
Chest X-ray and abdominal ultrasound	X		X ¹³		
Hematology & blood chemistries ¹⁴	X ¹⁵	X ¹⁶	X	CBC only	CBC only
Correlative blood samples ¹⁷	X	Day 15 only	X	X	X ¹⁹
Lactate dehydrogenase	X	Day 15 only	X		

Viral and host genotyping	X	
Urine pregnancy test	X ¹⁸	
Hepatitis B (for HIV-negative patients)	X	
CD4 and HIV RNA (if HIV positive)	X	X ¹⁹

¹ Screening assessments must be completed within 21 days prior to study enrollment.

² A window of +/- 7 days will apply to all study visits; however, lymph node measurements must take place prior to that cycle's treatment.

³ End-of-treatment visit should occur 7-14 days from final dose of chemotherapy. A subject who is being withdrawn for disease progression or for other reasons (e.g. unacceptable toxicity, etc.) should complete an end of treatment visit.

⁴ Long term follow-up will occur every 3 months until 24 months after the start of treatment unless otherwise noted.

⁵ After the initial visit (comprehensive history and physical exam) subsequent visits will address a focused history and physical exam.

⁶ All concomitant medications will be recorded.

⁷ See Appendix E. ECOG Performance Status

⁸ per NCI CTCAEv5.0 for notation of baseline toxicity. Assess from initial visit through first follow-up visit (12 weeks) and again at the final follow up visit (24 months).

⁹ Archival and/or fresh sample.

¹⁰ Survival will be assessed at each visit through out the duration of treatment, follow up, and long term follow up.

¹¹ Subjects with low risk disease will receive rituximab at 375 mg/m² weekly for 4 weeks. High risk subjects will receive rituximab at 375 mg/m² and etoposide at 100 mg/m² weekly for 4 weeks.

¹² Quality of life assessment includes PROMIS Global 10, MCD-SS and QoL will be assessed through follow up, and at 24 months during long term follow up. QoL will also be assessed at the time of any relapse.

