8.3 Assessment of Safety

Any subject who receives at least one dose of study therapy on this protocol will be evaluable for toxicity. Each subject will be assessed periodically for the development of any toxicity according to the Time and Events table. Toxicity will be assessed according to the NCI CTCAEv5.0.

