9.3 SAEs or Serious SARs

9.3.1 Timing

After informed consent but prior to initiation of study medications, only SAEs caused by a protocol-mandated intervention will be collected (e.g. SAEs related to invasive procedures such as biopsies, medication washout).

For any other experience or condition that meets the definition of an SAE or a serious SAR, recording of the event must begin from day 1 of study treatment and continue through the 30-day follow-up period after treatment is discontinued.

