10.2 Sample Size, Accrual and Duration of Accrual

To assess safety, toxicities will be monitored, graded, and documented by investigators at each clinic visit. Rituximab-based treatment will be considered safe in this population provided <40% non-hematologic AEs; we hypothesize that the true rate will be around 20%, based on previous studies.^{9,10,15,16} With a sample size of 24 patients, we reach 80% power to reject (if we observe $\leq 6 \geq$ Grade 3 AEs) the null hypothesis (H_0 : toxicity rate $>40\%$) using a one-sided exact test at $\alpha=0.1$. To account for 10% possible loss to follow-up during the toxicity-monitoring period, we will plan to enroll 27 patients. We plan to enroll approximately 10 patients annually and therefore expect to accrue patients for a total of three years.

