10.5 Secondary Objectives

10.5.1 To better characterize MCD presentation in Malawi.

Basic demographics and baseline laboratory values will be summarized using descriptive statistics (i.e., means, medians, and variability measures for continuous variable; rates and proportions for binary variables).

10.5.2 To describe the efficacy of the risk-adjusted approach as determined by clinical and radiologic response rates, 90-day, one-year, and two-year EFS and OS.

An event for EFS is either relapse (defined as “MCD attack” in the Inclusion Criteria (section 4.1)), refractory disease, lost-to-follow-up (LTFU), or death. We will consider patients LTFU if they cannot be contacted by phone for three months. Given the high mortality associated with MCD and previously published literature supporting a strong association between LTFU and mortality in SSA, we will consider LTFU as a failure event for both EFS and OS.⁴³ Relapse for purposes of this study will be defined as recurrence of an “MCD attack” (Inclusion Criteria; section 4.1) requiring re-initiation of treatment, with a strong preference for biopsy-proven recurrence whenever possible. We will conduct survival analysis using Kaplan-Meier methods. Radiologic response will be assessed in parallel with clinical response with response criteria defined in section 7.1.7. We will assess the prognostic value of radiologic response for EFS and OS in Cox proportional hazards model.^{10,15,16}

10.5.3 To describe the safety, as determined by the rate of all AEs during a risk-adjusted approach to treatment of MCD in Malawi.

All AEs will be described up to 30 days after final dose of MCD-directed treatment.

10.5.4 To describe the rate of KS exacerbation, as defined by symptomatic or clinical (dermatologic or visceral organ) exacerbation of disease.

The rate of KS exacerbation will be reported as the number of KS cases requiring KS-specific treatment divided by the number of patients with pre-existing KS (as defined by personal history of KS, baseline presence of KS, or KS in lymph node biopsy). This will be estimated along with a 95% confidence interval for the proportion.

10.5.5 To describe the quality of life of patients with MCD before, during and after treatment with a rituximab-based, risk-adjusted treatment approach, as assessed by the MCD symptom score⁴² and PROPr instrument.⁴⁴

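### Adverse-event recording rules stop about day 52, but the primary safety endpoint runs to 12 weeks (day 84), and the all-AE objective has two different windows

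*Combined protocol and SAP*

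**What the plan says.** **Passages that stop 30 days after treatment.**
- 9.2, non-serious events: "documentation must begin from day 1 of study treatment and continue through the 30-day follow-up period after treatment is discontinued".
- 9.3.1, serious events: "recording of the event must begin from day 1 of study treatment and continue through the 30-day follow-up period after treatment is discontinued".
- 10.5.3, analysis of the all-AE objective: "All AEs will be described up to 30 days after final dose of MCD-directed treatment".

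**Passages that run to 12 weeks.**
- 3.1, primary endpoint: Grade 3 or higher non-hematologic AEs and "treatment-related mortality through twelve weeks from the start of rituximab with or without etoposide therapy".
- 3.2.6: "Additional safety assessment will be graded by CTCAE v 5.0 through 12 weeks from the start of therapy".
- Table 7, footnote 8: toxicity evaluation from the initial visit to the 12-week visit, and once more at 24 months.

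**Passages that give other periods or no limit.**
- 7.1.5 has AEs captured for the whole study.
- The synopsis (1.1) speaks of one year of follow-up for toxicity.
- 10.2: "toxicities will be monitored, graded, and documented by investigators at each clinic visit".
- 8.3: "Each subject will be assessed periodically for the development of any toxicity according to the Time and Events table".
- 10.4.1, the primary analysis, names no window.

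No passage says which of these takes precedence.

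**The concern.** There are two separate problems.

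First, 3.2.6 and 10.5.3 serve the same all-AE objective (2.2.6) with different windows. A table to 12 weeks and a table to 30 days after the final dose can report different counts from the same data. This holds even if every site records perfectly.

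Second, the primary safety conclusion in 10.2 rests on at most 6 of 24 against a 40% null. If a site applies 9.2 and 9.3.1 as the cut-off, a patient whose only qualifying event falls between about day 53 and day 84 may never be entered. A missed event patient can only lower the count, both in the final test and in the AE row of Table 8. The error therefore always favours a finding of safety.

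After the week-5 visit, the 12-week visit is the only entry in the toxicity row of Table 7 that covers this interval. Staff there need one clear rule for an event with onset on, say, day 60.

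**Working it through.** **Inputs.** Doses on days 1, 8, 15 and 22 (Table 1); a 30-day recording limit (9.2, 9.3.1); a 12-week endpoint (3.1), taken as day 84; n = 24, null rate 40%, expected rate 20%, safe if at most 6, one-sided exact alpha 0.10, 10% loss (10.2). Section 10.2 words the criterion as a number of AEs. I read it as patients with at least one such event, which is what an exact binomial test requires.

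**1. The plan's own figures reproduce.**
- Error: P(X ≤ 6 | 24, 0.40) = 0.0960, below 0.10.
- Power: P(X ≤ 6 | 24, 0.20) = 0.811, stated as 80%.
- Enrolment: 24 / 0.90 = 26.7, rounded up to 27.

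**2. Size of the gap.** Recording ends on last dose day + 30; gap = 84 − that day.

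| Last dose (day) | Recording ends (day) | Days of the 12-week window left uncovered |
|---|---|---|
| 1 | 31 | 53 |
| 8 | 38 | 46 |
| 15 | 45 | 39 |
| 22 (on schedule) | 52 | 32 |
| 29 | 59 | 25 |
| 36 | 66 | 18 |
| 54 | 84 | 0 |

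On schedule, 52/84 = 62% of the window is covered. The gap is longest for patients who stop early. Counting 12 weeks as day 85 adds one day to each gap.

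**3. Effect on the 6-of-24 rule.** Let f be the share of event patients who go unrecorded. The documents do not give f, so it is an assumption shown over a range. The true 12-week rate is held at 40%, and q is the recorded rate. I use two models: a reduced cumulative hazard, q = 1 − 0.6^(1−f), and a reduced share of event patients, q = 0.40(1−f).

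| f | q, hazard | P(X ≤ 6) | q, event share | P(X ≤ 6) |
|---|---|---|---|---|
| 0 | 0.400 | 0.096 | 0.400 | 0.096 |
| 1% | 0.397 | 0.101 | 0.396 | 0.103 |
| 5% | 0.384 | 0.125 | 0.380 | 0.134 |
| 10% | 0.369 | 0.161 | 0.360 | 0.182 |
| 20% | 0.335 | 0.256 | 0.320 | 0.310 |

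**4. Allowing for capture at the 12-week visit.** If that visit captures a proportion c of patients with only late events, f = late share × (1 − c). With an assumed late share of 10%:
- c = 50% gives f = 0.10 × 0.5 = 5%, so the error is 0.12 to 0.13.
- c = 90% gives f = 0.10 × 0.1 = 1%, so the error is 0.101 to 0.103.

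**5. Worst case.** If every trial with exactly 7 event patients lost one, the error would be P(X ≤ 7 | 24, 0.40) = 0.192. That corresponds to f of 13.7% (hazard) or 10.9% (event share). At f = 5%, the chance that at least one of 7 is missed is 1 − 0.95^7 = 0.30, so 0.192 is an upper illustration and not an expected value.

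**The case against.** The best counter-argument is that the primary endpoint is defined without ambiguity in 3.1, and that enough other text supports collection to week 12. Sections 10.2, 8.3 and 7.1.5 and footnote 8 all point that way; 7.1.3 requires a symptom and toxicity history after screening; history and examination are scheduled at 12 weeks and every 3 months thereafter; and 10.4.1 has no 30-day limit. On this reading, 9.2 and 9.3.1 are a minimum. Late events are also probably a minority, because 6.1.6 says rituximab AEs are most common at the first infusion. An f of 10 to 20% would need that share of event patients to have no earlier qualifying event and also to be missed at week 12.

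Much of this stands. Under-counting is conditional on how sites read the text, the larger values of f deserve less weight, and the mortality component is largely protected because survival is checked at every visit and deaths are independently reviewed (5.3).

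It does not remove the conflict. Sections 9.2 and 9.3.1 do not call themselves a minimum, and 10.5.3 sets an upper limit. Assessing toxicity at a visit does not settle whether a day-60 event must be entered or reported as serious. Late onset is not excluded either: 6.1.6 gives 1 to 13 weeks for severe mucocutaneous reactions.

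One further reading is open. The treatment named in 10.5.3 might include therapy given after protocol treatment; if so, the section should say so.

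**Conclusion.** The concern holds and should be fixed. The conflict between 3.2.6 and 10.5.3 is definite and rests on no assumption. For the primary endpoint, the recording rules end 32 days before the endpoint window for a patient dosed on schedule, and up to 53 days before it for one who stops after the first dose. Whether events are lost depends on site practice, so the effect on the AE count is a one-directional risk. Its size depends on an assumed f: the error rises from 0.096 to 0.101–0.103 at 1%, 0.12–0.13 at 5% and 0.16–0.18 at 10%. Because 0.096 is already close to 0.10, even 1% takes the error past the nominal level. The sample size and decision rule themselves are sound.

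**What to change.** 1. In 9.2 and 9.3.1, set the end of recording as: *through 12 weeks from the start of treatment or 30 days after the last dose, whichever is later, for all treated patients*.
2. In 10.4.1, state that the primary AE endpoint counts events with onset through 12 weeks from the start of treatment, and that events recorded later are listed separately.
3. Give 3.2.6 and 10.5.3 one identical window: *through 12 weeks from the start of treatment*. If 10.5.3 was also meant to cover later MCD therapy, describe that as a separate listing.
4. In the synopsis, 7.1.5 and footnote 8, state which AEs are collected after that point and whether they enter any analysis. Footnote 2 allows visits 7 days either side, so also say how onsets between an early 12-week visit and day 84 are obtained.

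The cost is wording only. The 12-week toxicity visit already exists, and n = 24, enrolment of 27 and the 6-of-24 rule do not change. The added work is up to 32 more days of AE and SAE entry per patient last dosed on day 22, and up to 53 days for a patient who stops after day 1.

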9.3.2 Documentation and Notification

SAEs or Serious SARs must be documented and the NCCN project manager notified of the event/reaction via email within 24 hours of learning of its occurrence.

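### No toxicity contact is scheduled between end of treatment and week 12, and section 9 recording lapses at about day 52, although the primary safety endpoint runs to week 12

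*Combined protocol and SAP*

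**What the plan says.** Section 3.1 defines the primary endpoint as Grade 3 or higher non-hematologic AEs together with "treatment-related mortality through twelve weeks from the start of rituximab with or without etoposide therapy". Section 10.2 describes how they are found: "toxicities will be monitored, graded, and documented by investigators at each clinic visit".

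Table 7 (section 8.1) places toxicity evaluation at the initial visit, the four treatment days, end of treatment, week 12 and 24 months. Footnote 8 reads "Assess from initial visit through first follow-up visit (12 weeks) and again at the final follow up visit (24 months"). On the visit before the gap, footnote 3 says "End-of-treatment visit should occur 7-14 days from final dose of chemotherapy". No visit or call is listed between that one and week 12.

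Section 9 sets the recording periods. For non-serious AEs (9.2), "documentation must begin from day 1 of study treatment and continue through the 30-day follow-up period after treatment is discontinued", and "Documentation should occur at least monthly". For SAEs (9.3.1), "recording of the event must begin from day 1 of study treatment and continue through the 30-day follow-up period after treatment is discontinued", with notification "via email within 24 hours of learning of its occurrence" (9.3.2). Section 10.5.3 likewise describes AEs up to 30 days after the final dose, whereas 3.2.6 runs the additional safety assessment to 12 weeks.

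**The concern.** The endpoint, the contact schedule and the recording period do not cover the same time. The endpoint runs to week 12. The scheduled contacts stop at about week 5 and resume only at week 12. The duty to record under section 9 ends between the two.

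A Grade 3 or higher event in the gap that is not serious, or that is managed or ends outside a health facility, is first asked about at week 12, when it has to be dated, graded and attributed in retrospect. A patient lost after week 5 is not asked at all. Section 5.3 itself notes that deaths in this setting often happen away from health facilities and that diagnostic capability is limited, so spontaneous reporting is a weak substitute.

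The error runs one way. An event that is missed or graded too low reduces the count compared with the limit of 6 in 24, and so favours a conclusion of safety.

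**Working it through.** **The plan's own figure.** Inputs from section 10.2: 24 evaluable patients, null rate 40%, expected rate 20%, safe if 6 or fewer have an event, one-sided exact test at 0.1.
- Attained alpha = P(X ≤ 6 | n = 24, p = 0.40) = 0.096.
- Power = P(X ≤ 6 | n = 24, p = 0.20) = 0.811, against 80% stated.
- A cut-off of 7 would give alpha 0.192, so 6 is the right cut-off.
- 24 / (1 − 0.10) = 26.7, rounded up to 27 enrolled.

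The sample-size statement reproduces and is not in dispute. The attained alpha has almost no slack below 0.10.

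**The gap.** Count day 1 as the first dose, the last dose as day 22 (Table 1), and 12 weeks (84 days) after the start as day 85.
- End of treatment, 7-14 days after the last dose: day 22 + 7 = 29 to day 22 + 14 = 36.
- Gap on schedule: 85 − 36 = 49 to 85 − 29 = 56 days.
- Share of the window: 49/84 = 58% to 56/84 = 67%.
- With the ±7 days of Table 7 footnote 2 on the week-12 visit: 78 − 36 = 42 to 92 − 29 = 63 days.

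These figures assume dosing on schedule. Week 12 is counted from the start of treatment, so a dosing delay shortens the gap.

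**The section 9 recording period.**
- Close of the 30-day period: 22 + 30 = day 52.
- Part of it after end of treatment: 52 − 36 = 16 to 52 − 29 = 23 days.
- Part of the endpoint window after it: 85 − 52 = 33 days, or 33/84 = 39%.

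The monthly rule therefore reaches only 16-23 days past end of treatment, less than a month, and says nothing about the rest of the window.

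**Illustration of the bias.** The documents give no figure for missed events, so the share m is an assumption. With a true rate of 40%, the observable rate is 0.40 × (1 − m), and the chance of declaring safety is P(X ≤ 6 | 24, that rate):

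| Patients with events who are missed, m | Observable rate | P(6 or fewer of 24) |
|---|---|---|
| 0% | 40.0% | 9.6% |
| 2% | 39.2% | 11.0% |
| 5% | 38.0% | 13.4% |
| 10% | 36.0% | 18.2% |
| 20% | 32.0% | 31.0% |

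Even 2% missed takes the error above the stated 10%.

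**The case against.** A reader might infer that Table 7 breaks the monthly rule of 9.2 across weeks 5 to 12. The documents do not support that. The rule applies to non-serious AEs and ends about day 52, only 16-23 days after end of treatment, so no interval inside its period exceeds a month. It also concerns entry of events in the case report form and does not prescribe a visit.

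A reader might also infer that most of the primary result rests on recall at one visit. That too goes further than the text. Deaths do not depend on patient recall, and 5.3 has two non-study clinicians, with a tiebreaker, review all data on deceased patients. Many Grade 3 or higher events would meet the SAE definition and be notified once known. Section 7.1.5 says AEs are captured throughout the study and adds a patient-reported instrument. Share of calendar time is not share of events: 6.1.6 says rituximab reactions are commonest at the first infusion, and 1.3 says deaths often fall in the first month, which the weekly visits cover.

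All of this limits the size of the problem, but none of it creates a contact. SAE notification starts only when the site learns of the event, 7.1.5 gives no contact schedule, and the instruction in Appendix A to return with fever applies while chemotherapy is being given. Section 6.1.6 also names later events, such as mucocutaneous reactions with onset 1-13 weeks after exposure.

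Finally, a call does little for a patient who cannot be reached, and a day-57 call falls after the present 9.2 period has closed. Both points stand. The second is why the recording periods must change together with the schedule.

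**Conclusion.** The point holds as a mismatch between the endpoint and how it is ascertained. The primary window has a gap of 49-56 days on schedule (42-63 with the visit window) without a scheduled toxicity contact, and its last 33 days or so lie outside the recording periods of 9.2 and 9.3.1. The gap lengths follow from the documents, given on-schedule dosing.

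The direction of any bias is clear, toward declaring safety, but its size is not known. The range of 11% to 31% rests wholly on the assumed missed shares of 2% to 20% and on a true rate exactly at the 40% limit, so it should not be read as an estimate of the trial's error rate. The comparison also assumes that nothing is missed otherwise, which a call would not guarantee. The design calculation in 10.2 stands. This is a cheap improvement to ascertainment of the primary endpoint, together with an inconsistency in recording periods that needs resolving in any case.

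**What to change.** 1. In Table 7, add one telephone contact at about week 8 (around day 57) to the toxicity evaluation and survival rows, using the same CTCAE checklist as at visits. On schedule this splits the gap into 57 − 29 = 28 days (21 if end of treatment is day 36) and 85 − 57 = 28 days. Visit windows can lengthen either interval somewhat.
2. Extend the recording periods in 9.2 and 9.3.1 to 12 weeks from the start of treatment, to match 3.1, 3.2.6 and footnote 8, and reconcile 10.5.3 with 3.2.6. Without this step the call lies outside the section 9 periods.
3. State in 10.2 that events found at the telephone contact count toward the primary endpoint.

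The cost is about 27 calls by existing staff and a short amendment. Telephone contact is already the basis of the loss-to-follow-up rule in 10.5.2. Treatment, sample size and the test are unchanged. The downside is that the observed AE rate may come out slightly higher.
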